7.1 Inclusion Criteria

Subjects may be included that meet the following criteria:

Table 7.1-1: Inclusion Criteria

| Number | Inclusion Criteria |
|--------|--|
| IC - 1 | The subject is 18 years old or older at the time of providing consent. |
| IC - 2 | The subject will be available to attend all visits required in the trial and have an expected length of stay in the ICU no less than 3 days. |
| IC - 3 | The subject or his/her legally authorized representative is competent to sign the informed consent form |
| IC - 4 | The patient must have a central venous catheter (CVC) used on him/her, which may or may not be used in combination with other types of DVCs |
| IC - 5 | The patient's catheter insertion site is free of deformities, phlebitis, infiltrations, dermatitis, eczema, rashes, breaks, burns, tattoos, or other skin conditions that could affect the integrity of the skin at the insertion site |
| IC - 6 | The patient will comply with the DVC treatment process and the nursing process prescribed in this protocol |

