10.2.2 Visit 1/Enrollment Visit/Baseline Visit (Study Day 0)

The following procedures will be completed at Visit 1:

1. Confirmation of subjects' eligibility and assessment of inclusion/exclusion criteria;
2. Randomization of patients who met the inclusion criteria;
3. Assessment of the skin condition around the catheter site.
4. Performing immediate dressing changes at all DVC insertion sites based on subjects' conditions at enrollment, using either the subject device 3M™ Tegaderm™ CHG I.V. Securement Dressing or the 3M™ Tegaderm™ Transparent Film Dressing as per randomization results, and following routine departmental nursing procedures;

The following data will be collected at the first visit:

1. Demographic information (height, weight, gender, age at consent);
2. Past medical history and allergic history, collected according to HIS records: Collection of medical and allergic history within the last 3 months related to the inclusion/exclusion criteria, including but not limited to diabetes, immune-related diseases, skin conditions, etc.;
3. Vital signs: Pulse, blood pressure, respiratory rate, body temperature;
4. Relevant laboratory tests, including blood routine examination: Red blood cell (RBC) count, white blood cell (WBC) count, neutrophil ratio, hemoglobin, platelets, C-reactive protein, etc.;

5. DVC type, site of insertion, duration, documentation of any post-puncture exudation, application of any other products such as gauze, hemostatic pads, etc.;
6. Documentation of skin conditions around the catheter site, scoring with reference to the standards for evaluating local skin irritation as listed in the appendix;
7. Medication use in relation to the trial, including mainly fat emulsions, heparin, blood transfusions and antimicrobial drugs;
8. Adverse events, device defects, complaints.

10.2.3 Follow-up visits (number of visits to be marked if there are multiple visits during each dressing change)

Since the expected use duration of the test/control product is a maximum of 7 days, there will be at least one visit on the seventh day into the trial (if catheterization duration is longer than 7 days), and more visits could be taken on a case-by-case basis. The following procedures will be completed at Follow-up visits:

1. Performing dressing changes in accordance with routine departmental nursing procedures;

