19.4 Statistical Analyses

For patient baseline characteristics and demographic data, quantitative data will be analyzed based on t-test or rank sum test, and qualitative information will be analyzed based on Chi-square test or Fisher's exact test. CVC tip bacterial colonization rates, PICCO/hemodialysis catheter bacterial colonization rates, catheter-related bloodstream infection rates, and microbial species analysis will be analyzed by chi-square test or Fisher's exact test. Other results collected in this study, such as wearing duration, frequency of replacement, skin condition, and number of deaths, will be analyzed using t-tests or rank sum tests accordingly. The O'Brien-Fleming expenditure function will be used twice in succession to determine the test boundaries.

In addition, descriptive summaries of effectiveness and safety evaluation indicators will be presented for the entire trial and for subjects in each group. For continuous data, the data will be summarized by number of subjects, mean, standard deviation (SD), median, minimum and maximum values. For categorical data, they will be summarized by frequency and corresponding percentage.

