2.2 Secondary objective

The secondary objective of this study is to compare the differences in the following indicators between the test and control groups:

• Number of positive cases per 1,000 catheter-days of bacterial colonization at CVC tips

• Bacterial colonization rate at the tip of other types of (percutaneous) deep vein catheters and the catheterization site (number of culture positive cases/total catheters x 100% and number of positive cases per 1,000 catheter-days), including hemodialysis, PICCO, float catheters, etc.

 Incidence rate of Central Line Associated Bloodstream Infections (CLABSI) or Catheter Related Blood Stream Infections (CRBSI)

• Type of pathogenic microorganism (G+/G-/fungal or specific species, drug-resistant bacteria, etc.) and percentage of positivity

• Securement performance of the dressing: Frequency of dressing changes associated with wearing time and warping or peeling

• Effects on the skin of the covered area, e.g. local infection, local skin irritation

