6.2.2 General Information

- (1) Evaluation Indicators
 - 1) Demographic information: Age, gender, nationality, height and weight;
 - 2) General Condition: medical history, allergic history.
 - 3) Deep vein indwelling catheterization and peripheral skin evaluation status: Insertion site, insertion type, duration of insertion (days), with or without blood oozing after puncture placement, whether other products were applied, whether emergency insertion was performed, whether skin assessment around the insertion site was performed, skin assessment around the insertion site (including erythema, edema, pruritus score and whether skin infection was diagnosed);
 - ♦ Methodology for calculating relevant indicators:
 - ✓ Age (years) = (date of informed consent date of birth + 1) / 365.25, rouding to whole numbers
 - ✓ Duration of tube insertion (days) = date of randomization date of tube insertion + 1
- (2) Evaluation method

FAS was used for evaluation.

The demographic data, general conditions were described accordingly to their numerical characteristics and quantitative indicators were compared between the two groups of participants using t-test/Wilcoxon rank sum test; qualitative indicators were compared between the two groups of participants using chi-square test/Fisher exact probability method.

Summary of the evaluation of deep vein indwelling catheterization and surrounding skin at the level of the insertion site. The two groups of quantitative indicators were compared using t-test/Wilcoxon rank sum test according to their corresponding numerical characteristics description; and the two groups of qualitative indicators were compared using chi-square test/Fisher exact probability method.

In addition, a list of data on medical history, allergic history, deep vein indwelling catheterization prior to enrollment and skin evaluation around the insertion site, and previous/concomitant medication was made for both groups of participants.

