6.3 Efficacy Evaluation

6.3.1 Primary Efficacy Evaluation

(1) Evaluation Indicators

Occurrence rate of bacterial colonization of the CVC tip segment and skin at the insertion site after extubation (number of culture-positive cases/total catheters × 100%)

Primary endpoint: Positive rates of catheter tip cultures and sampling cultures of skin surrouding the insertion site in patients with deep vein indwelling catheterization after CVC tubes were removed.

(2) Evaluation method

FAS and PPS were used for both total catheter count and participant level evaluation. If more than one catheter of the same type was available for the same participant and the culture results were inconsistent, a positive culture result was taken for that participant when participant-level analysis was performed.

Describe the number and percentage of cases of bacterial colonization of the CVC tip segment and skin at the insertion site after extubation in both groups, and compare the two groups using a chi-square test or Fisher's exact test.

In addition, because some subject may have two or more than two CVC, which are interrelated, a generalized mixed linear model was developed to evaluate the difference in the occurrence rate of bacterial colonization between the two groups, using the occurrence rate of bacterial colonization of the CVC tip segment after extubation and the occurrence rate of bacterial colonization of the skin at the CVC insertion site after extubation as dependent variables, group as a fixed effect, and insertion site, skin infection of baseline insertion site, and their interaction as random effects, respectively.

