All adverse events during the study, adverse events leading to study discontinuation, adverse events leading to death and serious adverse events will be detailed in the list.

Describe separately vital signs and baseline variation at the baseline and the last (i.e., end of treatment or withdrawal from discontinuation visit) visit and compare the two groups with t-test.

All tests completed at the last visit and descriptive statistics were listed for laboratory examination in the form of a pre- and post-treatment cross-tabulation (normal/abnormal results determined according to the range of normal values). A list of laboratory examination that appear abnormal after treatment, including random number, treatment group, test time point, item, measured value, and normal value range.

Qualitative descriptive statistics were used to describe separately erythema, erythema, pruritus score and skin infection at the baseline and last (i.e., end of treatment or withdrawal discontinuation visit) visit at different insertion sites in two groups and compare the two groups using the chi-square test or Fisher's exact test.

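### SAP 6.4 compares the scored skin outcomes between arms by insertion site only; it needs one overall comparison per participant

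*SAP*

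**What the plan says.** SAP 2.2 and Protocol 5.2 list the skin outcome among the secondary objectives to be compared between groups: "Effects on the skin of the covered area, e.g. local infection, local skin irritation". SAP 4.2 places it under the safety indicators.

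The planned comparison is in the last paragraph of SAP 6.4. Erythema, pruritus score and skin infection at baseline and at the last visit are described "at different insertion sites in two groups and compare the two groups using the chi-square test or Fisher's exact test". The word erythema is printed twice in that list. SAP 6.2.2 lists erythema, edema and pruritus for the same assessment, so the second is probably meant to be edema. SAP 6.2.2 uses the same unit at baseline: "Summary of the evaluation of deep vein indwelling catheterization and surrounding skin at the level of the insertion site".

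Several sites per participant are foreseen. Protocol 7.1 (IC-4) requires a CVC, "which may or may not be used in combination with other types of DVCs". At enrolment, Protocol 10.2.2 calls for "Performing immediate dressing changes at all DVC insertion sites", all with the allocated dressing. Note 1 to Protocol Table 10.3-1 expects several end-of-treatment visits when catheters are removed in succession.

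Elsewhere the SAP deals with several records per participant. For the primary endpoint, SAP 6.3.1 states that "FAS and PPS were used for both total catheter count and participant level evaluation", counts a participant as positive if any catheter of the type is positive, and gives the reason that "some subject may have two or more than two CVC, which are interrelated". SAP 6.3.2 has a participant-level analysis for the other catheters. SAP 6.4 counts repeated adverse events once per participant, at the greatest severity.

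Protocol 19.4 assigns t-tests or rank sum tests to "Other results collected in this study, such as wearing duration, frequency of replacement, skin condition, and number of deaths", without naming the unit of analysis.

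**The concern.** The randomised unit is the participant, but the only between-arm test of the scored skin outcomes is organised by site. The SAP gives no rule for combining a participant's sites and no allowance for clustering. The sentence in SAP 6.4 can be read in two ways.

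- **One table per anatomical location.** Each test uses only the participants with a catheter there, and no result covers the whole trial. A real difference in skin reactions between the dressings is easier to miss.
- **One record per site.** The chi-square or Fisher test treats two or three sites on one participant as independent. If reactions tend to occur together within a participant, the p-value is too small.

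In both cases a listed secondary objective lacks a single overall between-arm answer on the scored outcomes. The unit of analysis would also be settled after the data are in.

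**Working it through.** **Inputs.** From the documents: a two-sided level of 0.048 at the final analysis (SAP 6.1), and 220 per arm with 1:1 allocation (SAP 3.2 and 3.3). The documents give no skin-reaction rate, power, number of sites per participant or within-participant correlation, so there is no skin figure of the plan's own to reproduce. All rates, site counts and correlations below are assumptions. The 220 is used only as the arm size, as if every participant were in the safety set.

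**Reading 1: separate tables by location.** Power at 0.048, by exact binomial enumeration, for assumed rates of 10% v 3%:

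| Participants per arm in the table | Fisher | Chi-square |
|---|---|---|
| 220 (all) | 82% | 87% |
| 110 (one half) | 45% | 57% |
| 73 (one third) | 27% | 38% |
| 44 (one fifth) | 10% | 24% |

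A second illustration uses 5% v 12%, a normal approximation and an assumed 50/30/20% split over three locations. Power falls from 75% overall to 45%, 29% and 21%. With three independent tables at 0.048, the chance of at least one false positive for one outcome is 1 − 0.952³ = 13.7%.

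**Reading 2: one record per site.** With m sites per participant and intraclass correlation ICC, the design effect is

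DE = 1 + (E[m²]/E[m] − 1) × ICC,

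and the real level of the nominal 0.048 test is 2 × (1 − Φ(1.977/√DE)), where 1.977 is the two-sided 0.048 critical value.

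Example: 20% of participants have two sites and the rest one. Then E[m] = 0.8 + 0.4 = 1.2 and E[m²] = 0.8 + 0.8 = 1.6, so the ratio is 1.333. At ICC 0.3, DE = 1 + 0.333 × 0.3 = 1.10 and 1.977/√1.10 = 1.885, which gives 0.059. At ICC 0.9, DE = 1.30 and 1.977/√1.30 = 1.734, which gives 0.083.

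| Share with several sites | Sites each | DE, ICC 0.3 to 0.9 | Real level (formula) | Real level (simulation) |
|---|---|---|---|---|
| 0% | 1 | 1.00 | 0.048 | 0.043 to 0.049 |
| 20% | 2 | 1.10 to 1.30 | 0.059 to 0.083 | 0.060 to 0.083 |
| 50% | 2 | 1.20 to 1.60 | 0.071 to 0.118 | 0.071 to 0.121 |
| 80% | 2 | 1.27 to 1.80 | 0.079 to 0.141 | 0.079 to 0.141 |
| 20% | 3 | 1.26 to 1.77 | 0.078 to 0.137 | 0.075 to 0.136 |
| 50% | 3 | 1.45 to 2.35 | 0.101 to 0.197 | 0.100 to 0.196 |
| 80% | 3 | 1.55 to 2.66 | 0.113 to 0.225 | 0.110 to 0.227 |

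The simulation used 220 participants per arm, a 10% reaction rate in both arms and 20,000 runs per row and ICC value. At ICC 0, DE is 1 and there is no inflation, whatever the number of sites.

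**After the fix.** In the same simulations, a participant-level test (any site reacting) had a real level of 0.043 to 0.050 throughout.

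**The case against.** Much of the case on the other side stands.

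- A reader might infer that the trial cannot say what share of participants on each dressing had a skin reaction. The documents do not support that. Protocol 3.3.2 lists erythema, rash, irritation, itching and local infection as anticipated device effects, and Protocol 11.4 makes these effects reportable. SAP 6.4 tabulates adverse events by arm with percentages, once per participant. That table has no between-arm test, and nothing says that a given score becomes an adverse event, so the gap remains for the scored outcomes.
- A reader might infer that the false-positive rate is well above 0.048. That is not established. It depends on how many participants have several sites, which the documents do not say, and it is nil if all have one.
- The wording of SAP 6.4 most naturally means tables by location, and SAP 6.1 takes people as the default denominator. Such tests are valid if each participant contributes at most one site per table. The loss is then power and an overall result, not validity. SAP 6.2.2, with its site-level summary, leaves the other reading open.
- A high correlation is an assumption. Local infection may well be specific to a site, and the device precautions in Protocol 3.0 name local causes of skin irritation or trauma, such as residue on the skin and stretching of the dressing.
- The table shells are in a separate file (SAP 9), so an overall row may exist there. The SAP text does not call for one.
- Protocol 19.4 does list a test of skin condition, but without a unit and of a different type, so it does not fill the gap.

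**Conclusion.** The concern holds for the scored skin outcomes and skin infection. SAP 6.4 gives no overall participant-level comparison of them, although the SAP has participant-level rules for cultures and adverse events.

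The size depends on the reading and on quantities the documents do not give. Under separate tables, the cost is the missing overall result and lower power: from 82% to 45% or 27% if a table holds a half or a third of the participants, at assumed rates of 10% v 3%. One dominant location would cost less. Under pooled sites, the real level runs from 0.048 with single sites, through about 0.06 to 0.08 (20% with two sites) and 0.07 to 0.12 (50% with two), to higher values with three sites.

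This is a secondary, safety-related matter with no stated hypothesis or power. The primary analysis and the 440 participants are unaffected. It is worth correcting because the correction is cheap and fixes the unit before results are seen.

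**What to change.** In SAP 6.4:

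1. For each of erythema, edema, pruritus and skin infection, add one overall between-arm comparison in the safety set with the participant as the unit. Use the worst score, or any infection, across the participant's study-dressed sites, taken at the last assessment of each site. Naming the time point matters because catheters may come out at different visits.
2. Optionally, add the worst post-baseline score over all dressing-change and end-of-treatment visits. The last visit alone misses reactions that have resolved, and the scores are already recorded at each change (Protocol 10.2.3 and Table 10.3-1).
3. Keep the by-site tables as description. If site-level p-values are wanted, take them from a GEE or mixed model with participant as the cluster.
4. Correct the repeated erythema against the list in SAP 6.2.2.
5. Reconcile the chi-square/Fisher test with the t-test or rank sum test in Protocol 19.4, and name one test per outcome.

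The cost is SAP wording and one derived variable per outcome (two with the optional analysis), with no new data and no extra participants. The small downside is that a worst-site summary does not show which site reacted; the retained by-site tables do.

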7. DATA PROCESSING AND CONVERSION

7.1 Missing severity of adverse events

Missing severity of adverse events before randomization will be filled using "moderate". Missing severity of adverse events that occur after randomization will be filled using "severe" and these filled values will be used for occurrence rate summaries only and will be presented as original values in the final list.

7.2 Missing relationship between adverse events and device

Missing relationship between adverse events occurring after randomization and investigational device will be filled in using "relevant", and these filled-in values will be used for occurrence rate summary only and will be presented as original values in the final list.

7.3 Missing primary efficacy endpoint

Missing primary efficacy endpoint will be filled using the WCCF (i.e., filled as "positive"), while, at the same time, giving the result of not filling.

8. INTERIM ANALYSIS

The interim analysis will be performed when enrollment reaches 220 participants, and this interim analysis will be performed by an unblinded team (including statisticians

and programmers) to recalculate the total sample size needed to adjust this study based on the results of the primary endpoint of 220 participants already enrolled and the dropout rate. If the results of the interim analysis show that: When the difference of the primary endpoint between the two dressings, i.e., the positive rate of bacterial culture of the CVC tip segment and skin at the insertion site (either one), is greater than 50% and the p-value is less than 0.005, and with all other considerations to support the objectives and the assumptions of the study were met, the study will be discontinued early with a final statistical analysis report. Otherwise, only issue: The decision to continue as per the protocol or to increase the sample size at a later stage; meanwhile, specific analytical findings were maintained blinded until the entire study was unblinded for final analysis. If the sample size recalculated for the interim analysis was less than or equal to that specified in the protocol, the final analysis was performed when the subsequent test was conducted to the sample size specified in the protocol; if the sample size recalculated for the interim analysis exceeded that specified in the protocol, the final analysis was performed when the subsequent test was conducted to the re-estimated sample size.

In accordance with the O'Brien-Fleming expenditure function, all statistical tests for this interim analysis were two-sided, and p-values less than 0.005 were considered statistically significant for the differences tested.

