9.2 Point of Exit

Study subjects may exit the study for a variety of reasons. The Investigator shall record the reason for withdrawal and discontinuation of the study in the applicable Case Report Form. These reasons include, but are not limited to:

- Study completion (all study related visit(s) are completed)
- Withdrawal by the Subject
- Withdrawal by Investigator
- Lost to follow-up
- Death
- Study Termination

If a subject withdraws or discontinues participation before study completion, the subject will not be accounted into the per protocol set (PPS) analysis until the required enrollment is reached but will be accounted into the safety set analysis.

[figure not shown]
Data collected until the last known contact of study subject may be used in the analysis of study data. Because the subjects in this study are all ICU patients, patients will be considered lost to follow-up if they are transferred out of the ICU or discharged without removal of the CVC. If the study subject withdraws from the study for any reason and there is an ongoing safety event, additional safety event information may need to be collected by the Investigator and shared with Sponsor.

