19.5 Planned Interim Analyses and Criteria for Clinical Investigation

Interim analysis will be conducted at enrollment to 220 subjects, and the total CVC tip colonization rate obtained from the interim analysis will be used to recalculate and evaluate the sample size.

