6. STATISTICAL ANALYSIS METHODS

6.1 General Principles

Statistical analyses will be performed using SAS 9.4.

In accordance with the O'Brien-Fleming expenditure function, all statistical tests in the final analysis were two-sided, and a p-value of less than 0.048 would be considered statistically significant for the difference being tested (except where specially described).

The description of quantitative indicators will calculate the number of cases (missing), mean, standard deviation, median, minimum, and maximum. The minimum and maximum values will have the same decimal digits retained as the raw data, but the mean, standard deviation, and median will have one more decimal digits than the raw data. However, generally the maximum number of raw data will not exceed four decimals.

The description of qualitative indicators will use the number of cases and percentages of each category. Calculation of percentage was based on non-missing data in the analysis set. Percentage was rounded to one decimal number. Unless special instruction, percentages will be calculated using the number of people in the corresponding group for each population as the denominator.

All numerically derived variables will keep two decimals, unless otherwise specified.

The treatment of missing data will be described in a separate section, otherwise all missing data will not be filled.

Missing days in the date will be filled using 1 day, and missing months will be filled using 1 month, as a general principle for filling missing dates, unless special instruction.

Baseline will be defined as the last test value prior to treatment.

Change relative to baseline in this paper will be defined as post-treatment minus baseline.

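### Protocol 19.5 and SAP 8 name different inputs for re-estimating N, and SAP 8 sets no maximum and does not exclude the arm difference, so 5% error is secured under one reading but not under another

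*SAP*

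**What the plan says.** - **Re-estimation input, Protocol 19.5:** "the total CVC tip colonization rate obtained from the interim analysis will be used to recalculate and evaluate the sample size". Neither an arm-level effect nor a dropout term appears.
- **Re-estimation input, SAP 8:** an unblinded team works out a new "sample size needed to adjust this study based on the results of the primary endpoint of 220 participants already enrolled and the dropout rate". The SAP's primary endpoint covers both the CVC tip and the insertion-site skin.
- **Direction of change, SAP 8:** if the recalculated N is no larger than planned, the planned N stands. If it is larger, "the final analysis was performed when the subsequent test was conducted to the re-estimated sample size". No maximum is given.
- **Final test:** SAP 6.1 sets the level ("a p-value of less than 0.048 would be considered statistically significant for the difference being tested"). SAP 6.3.1 says to "compare the two groups using a chi-square test" or Fisher's exact test. SAP 8 itself gives only the interim level, 0.005. No combination test or adjusted boundary is described for an increased N.
- **Missing cultures:** SAP 7.3 states "Missing primary efficacy endpoint will be filled using the WCCF", meaning as positive, and also reports the unfilled result. Under Protocol 9.2, "patients will be considered lost to follow-up if they are transferred out of the ICU or discharged without removal of the CVC".
- **Unit:** in SAP 6.3.1, "FAS and PPS were used for both total catheter count and participant level evaluation".

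**The concern.** The two texts permit different rules. A nuisance-parameter rule (pooled rate, fixed effect) leaves the group-sequential levels essentially intact. A rule that sets N from the observed arm difference does not, if the accumulated data are then tested as though N had been fixed. SAP 8 gives the arm results to the team that recalculates N and does not say which kind of rule applies. A reader of a final p-value just under 0.048 could not tell whether the 5% claim holds.

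There is a secondary gap. SAP 8 does not say whether cultures filled as positive enter the interim rate. If they did, the rate would look higher than it is, and N would fail to rise in the low-rate case that re-estimation is meant to catch.

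The stopping condition in SAP 8 also leaves open whether tip and skin form a composite or two alternative endpoints, which is a further reason to name the tip rate.

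**Working it through.** **Inputs from the documents.** Control rate 18.7%, 50% relative reduction (so 9.35%), 80% power, 5% overall, 220 per arm (Protocol 19.2, SAP 3.2). 1:1 allocation (SAP 3.3). Interim at 220 participants, so 110 per arm, at 0.005 (SAP 8). Final level 0.048 (SAP 6.1).

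**1. The plan's own figures.** With critical values c1 = 2.807 (p = 0.005) and c2 = 1.977 (p = 0.048) and correlation √0.5 between looks, overall error is

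1 − P(|Z1| < c1 and |Z2| < c2) = 0.0499.

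The pair is therefore right for N fixed at 440. For the sample size,

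n = [z₁₋α/₂ √(2p̄(1−p̄)) + z₀.₈ √(pC(1−pC) + pT(1−pT))]² / (pC − pT)².

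At α = 0.048 and p̄ = 0.14025 this is (1.977 × 0.4911 + 0.8416 × 0.4866)² / 0.0935² = 218.02, so 219 per arm. With the continuity correction that the text names, it is 239. The planned 220 matches the uncorrected form.

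**2. The input changes N.** Take a pooled rate of 14.0% and the same formula at α = 0.05. Holding the 50% reduction gives 216 per arm (432 in total). Using observed arm rates of 16.8% and 11.2% gives 601 per arm (1,202 in total).

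**3. Type I error.** Simulation, 1,000,000 trials per scenario, null rates 14% and 18.7%. Assumed rule, since the documents give none: stop at p < 0.005; otherwise apply the formula above, never below 220 per arm and never above the cap; final test on all data at 0.048.

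| Rule | Cap per arm | Uncorrected test | Continuity-corrected test |
|---|---|---|---|
| Fixed N | – | 4.9-5.1% | 3.6-3.7% |
| Pooled rate, 50% held | 330 or 440 | 5.0-5.1% | not run |
| Observed arm rates | 330 | 5.5-5.6% | below 5% |
| Observed arm rates | 440 | 5.9% | below 5% |
| Observed arm rates | 660 | 6.3-6.4% | 5.0-5.2% |
| Observed arm rates | 5,000 (effectively none) | 7.0-7.1% | 5.9-6.0% |

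Variants of the arm-rate rule, uncorrected test:
- N raised only for a trend favouring CHG: 5.2-5.4%.
- N raised only when conditional power is at least 50%: 4.8-4.9%.
- Planned N kept when the recalculated N exceeds a cap of 330 or 440 per arm: 4.8-5.0%. This protection also depends on the cap; with a cap of 4,400 in total it is about 5.3%.
- Early stopping also requiring a relative difference above 50%: 5.6-6.0% at caps of 330 and 440.

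**4. Filled positives (secondary).** Missing fractions f of 5%, 10% and 20%, equal in both arms, are assumptions. With true control rate 14% and test rate 7%, the pooled rate is r = 0.105. The filled rate is r(1 − f) + f, the implied control rate is that divided by 0.75, and the test rate is half of the control rate.

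| f | Rate used | Implied control | n per arm |
|---|---|---|---|
| 0 (observed cultures) | 0.1050 | 14.0% | 304 |
| 5% | 0.1498 | 20.0% | 202 |
| 10% | 0.1945 | 25.9% | 147 |
| 20% | 0.2840 | 37.9% | 89 |

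Every filled figure is below 220, so N would stay at plan when the formula on observed cultures asks for 304. At 14% control, 10% missing and a maximum of 440 per arm, N rises in 98% of simulated trials with the observed rate and in 2-4% with the filled rate. Power of the unfilled analysis is 81% against 63%.

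**The case against.** A reader might infer that the trial will set N from the unblinded effect, or that its error rate is above 5%. The documents do not support either. Protocol 19.5 names the total tip rate, and SAP 9 presents the SAP as a more detailed account of the protocol. The phrase about primary-endpoint results can be read as that same rate. In SAP 8 the difference between dressings appears only in the stopping condition, and an unblinded team is needed for that test anyway. All of this stands, so the inflation is conditional.

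Nor is there simply no formula. Protocol 19.2 and SAP 3.2 supply the test, effect, power and level, and they count patients, so the natural reading is the same calculation with a new rate and the participant as unit. That stands too. What is missing is a statement that the 50% reduction is held, and a maximum N.

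On filling, SAP 8 lists dropout as a separate input, which suggests that missing outcomes are dealt with there. No passage says that filled values enter the rate, so that harm rests on an unstated rule and assumed missing fractions.

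The objection does not remove the conflict between the two input descriptions, or the fact that one permitted reading of SAP 8 breaks the 5% claim.

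**Conclusion.** The point holds as an unresolved inconsistency with a conditional consequence, and it should be fixed. Under the Protocol 19.5 input the stated levels hold about 5.0-5.1%. Only if observed arm rates set N does two-sided error with the uncorrected test rise to about 5.5-5.6% (330 per arm), 5.9% (440 per arm) or about 7% with effectively no maximum. A continuity-corrected test protects at 330-440 per arm but not at larger maxima, and SAP 8 states none. These sizes rest on the assumed re-estimation rule and on the interim falling at 110 per arm with outcomes known. The filling effect is secondary and depends on the assumed missing fractions.

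**What to change.** Before interim data are seen, reconcile SAP 8 with Protocol 19.5:

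- Repeat the Protocol 19.2/SAP 3.2 calculation with the pooled, arm-blind CVC-tip positive rate among participants with an observed tip culture.
- Hold the 50% relative reduction.
- Apply dropout once, as n/(1 − dropout).
- Allow increases only, up to a stated maximum N.
- Keep 0.005 and 0.048 for the efficacy tests.

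If an effect-based increase is intended, pre-specify its rule and maximum N, and test with a pre-weighted stage-1/stage-2 combination (weights √0.5) at the same levels. Simulated error is then about 5.0%.

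The cost is a change to the SAP wording and a protocol sentence, with approval as required and staff training under Protocol 21.0. No new data are needed. There are three downsides:

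1. N does not rise for a smaller true effect. At a 35% reduction power is 49%, against 68% with the combination test (both at most 440 per arm).
2. Accrual lengthens. At the planned 440/15 = 29.3 per month, 330 per arm takes 660/29.3 = 22.5 months and 440 per arm takes 880/29.3 = 30 months. With no missing data, power at control rates of 18.7%, 14% and 10% is 81%, 67% and 52% at fixed N; 84%, 80% and 68% with a maximum of 330 per arm; and 84%, 82% and 78% with 440.
3. The rule sizes the unfilled analysis. The primary WCCF-filled FAS analysis stays underpowered when cultures are missing: at 14% control and 10% missing it has 55% power, against 38% at fixed N.
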